12.1 Early Discontinuation of the Study Treatment

A subject may be discontinued from study treatment at any time if the subject, the investigator, or the Sponsor feels that it is not in the subject's best interest to continue. The following is a list of possible reasons for early discontinuation of study treatment:

- Subject or subject's legal representative decision
- Adverse event
- Protocol violation
- Death

If a subject is discontinued from treatment due to an adverse event, the subject will be followed and treated by the Investigator until the abnormal parameter or symptom has resolved or stabilized.

All subjects who discontinue study treatment early will be evaluated for an early discontinuation of study treatment visit as soon as possible and then encouraged to complete all remaining scheduled visits and procedures.

12.2 Withdrawal of subjects from the study

All subjects are free to withdraw from participation at any time, for any reason, specified or unspecified, and without prejudice. This may include subjects who withdraw from study treatment early and who decline to continue to come in for remaining follow-up

visits or it may include subjects who completed treatment and decline to come in for remaining follow up visits.

Reasonable attempts will be made by the investigator to provide a reason for subject withdrawals. The reason for the subject's withdrawal from the study will be specified in the subject's source documents. Subjects who withdraw from the study should be encouraged to come in for a final visit (and the procedures to be followed would include those for an early discontinuation visit).

12.3 Replacement of subjects

Subjects who discontinue or are withdrawn from the study before completing Visit 2 may be replaced at the discretion of the study investigator team.

13. Protocol violations

A protocol violation occurs when the subject, investigator, or the Sponsor fails to adhere to significant protocol requirements affecting the inclusion, exclusion, subject safety and primary endpoint criteria. Protocol violations for this study include, but are not limited to, the following:

- Failure to meet inclusion/exclusion criteria
- Use of a prohibited concomitant medication. Subjects requiring additional non-nephrotoxic antibiotics to treat pulmonary exacerbation will be asked to continue in the study and this will not be treated as a protocol violation.

Failure to comply with Good Clinical Practice (GCP) guidelines will also result in a protocol violation. The sponsor will determine if a protocol violation should result in early discontinuation of study treatment for a subject.

When a protocol violation occurs, it will be discussed with the investigator and a Protocol Violation Form detailing the violation will be generated. This form will be signed by a Sponsor representative and the Investigator. A copy of the form will be filed in the study regulatory binder and in the Sponsor's files. The site will report the violation to their IRB in accordance with the IRB reporting requirements.

14. Data Safety Monitoring

A Data Safety and Monitoring Plan (DSMP) is in place for this study.

Safety data will be monitored on a continual basis throughout the trial by [name]. Efficacy will be evaluated in two planned interim analyses, each of which will occur after 1/3rd of the data is accrued or 1/3rd of the participants have completed dosing. Safety monitoring will include monitoring of serious adverse events, adverse events, participant withdrawals, safety data, and enrollment summaries.

Serious adverse events will be monitored by [name] on an ongoing basis throughout the study. When approximately 50% of patients have completed the study through Visit 4, an interim analysis for safety, futility, and early significance will be conducted

[name] will monitor adherence to the protocol on a continual basis. If deviations occur, the PI will discuss with study staff any issues that may be causing these deviations and ways to improve adherence to the protocol. Deviations will be reported to the IRB in accordance with the IRB reporting requirements

[name] will monitor the data collection for accuracy and quality for the study. Data will be collected from subject medical and research records and maintained in electronic Case Report Forms (eCRFs) using REDCap (Research Electronic Data Capture), a secure web-based application that supports data capture for research studies.

15. Statistical Methods and Considerations

15.1 General: Summary statistics will be calculated for demographic and baseline characteristics (age, sex, genotype, diabetic status, FEV₁ % predicted) time to therapeutic dosing for PK-adjusted colistin versus tobramycin, number of therapy interruptions between study arms, and total number of IV antibiotic doses. Study medications and exposure to study drug data will be summarized in contingency tables. Summary statistics and changes from admission visit to end of treatment will be presented for FEV₁ % predicted and questionnaire results, on an intent-to-treat basis, including all subjects receiving at least three days of colistin or tobramycin, and at least one efficacy assessment. Subjects will be enrolled once.

15.2 Efficacy analysis: We will perform equivalence testing to show similarity of colistin treatments, as well as for colistin vs tobramycin treatments. For both comparisons, confidence intervals for difference in FEV₁ changes from pre to post treatment time points will be constructed, and equivalence tests to within 5% will be performed. These will be derived from linear mixed models fitted for FEV₁ that include a random intercept for subjects to account for repeated measures, and the following covariates: age, other medication, admits in the previous year, and diabetes. Nested random terms will be included in the model to account for repeated measures – one for subject and one for visit within subject. CFQ-R domain scores will be analyzed in a similar fashion. Times to next pulmonary exacerbation and occurrence of neurotoxicity between standard colistin and PK-adjusted colistin will be analyzed using the Kaplan-Meier method. Subsequent pulmonary exacerbations in the ensuing year for all enrolled subjects, as well as antimicrobial resistance to tobramycin and colistin before and after treatment, will be summarized. Unless otherwise noted, 2-sided tests will be used with $\alpha = 0.05$.

15.3 Safety analysis: The safety profile of each colistin arm and the tobramycin arm will be assessed in terms of the following: incidence of acute kidney injury (AKI), incidence of treatment related clinical events (ototoxicity, vestibular toxicity, and neurotoxicity). Adverse event rates will be compared between treatment groups using logistic regression, adjusting for age, medications such as vancomycin, baseline FEV₁, admits in the previous year, exposure to nephrotoxic antibiotics in the previous 5 years, and diagnosis of CF related diabetes (CFRD) as covariates. Repeated measures within subjects will be accounted for by including a random intercept for subjects. Summary statistics and changes from admission will be presented for serum creatinine and urine:protein ratios. The urine protein:creatinine ratio will be assessed as a

biomarker of drug toxicity. There are no published criteria for cessation of therapy or accurate prediction of AKI as a result of the urine protein values. Thus, this data will be analyzed as a predictor for AKI. We will analyze Nephrocheck® assay results in a case control design. Subjects who develop AKI within each of the study arms will have urine thawed and analyzed by Nephrocheck® and those results will be compared to age, gender, and FEV₁ matched control urines obtained from subjects within the study who did not develop AKI. An adjusted odds ratio will be derived from a model fitted with unconditional logistic regression and adjusted for confounding variables. Estimates of odds ratios and 99% confidence intervals will be presented.

15.4 Sample size and power: The original power calculations estimated 90 subjects per arm in order to achieve power to demonstrate efficacy, or higher FEV₁ in a tobramycin versus colistin study arm. Since preliminary data demonstrates that colistin is safer than tobramycin in terms of kidney injury, the more appropriate power calculation would evaluate colistin superiority for safety. In a retrospective cohort 500 subjects, FEV1% improvement after tobramycin treatment during exacerbation therapy was 3% higher than in those receiving colistin; however, rates of acute kidney injury (rise in serum creatinine ≥ 0.3 mg/dL while on therapy) were 60% higher in tobramycin treated subjects versus standard colistin treated subjects. Since no preliminary data was available on less frequent colistin dosing, which theoretically would lead to less frequent episodes of kidney injury, we estimate we are powered to identify a safer method for dosing colistin with samples of 30 subjects per group, though we may be underpowered to find a significant FEV₁ difference between groups.

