PRIMARY ENDPOINT	
 1. Absolute change in FEV₁ % predicted with standard colistin TID dosing versus PK-adjusted colistin BID dosing, with APE treatment. 2. Absolute change in FEV₁ % predicted with standard tobramycin daily dosing versus PK-adjusted colistin BID dosing, with APE treatment. 3. Absolute change in FEV₁ % predicted with standard tobramycin daily dosing versus standard colistin TID dosing. 4. Safety of standard colistin TID dosing versus PK-adjusted colistin BID dosing in APE treatment, based on assessments of clinical symptoms, AKI occurrences during treatment (based on KDIGO criteria), change in urine protein:creatinine ratios, and an FDA approved renal injury biomarker test, Nephrocheck®, which measures: TIMP2 and IGFBP-7 (Astute Medical). 4. Safety of standard tobramycin daily dosing versus PK-adjusted colistin BID dosing and standard colistin TID dosing in APE treatment, based on assessments described in #3.

SECONDARY ENDPOINTS	
 1. Time to therapeutic dosing and number of therapy interruptions due to changes in creatinine with standard colistin, modified colistin, and standard tobramycin dosing. 2. Total number of IV doses delivered over the course of APE treatment. 3. Change in sputum microbiology profile following treatment with colistin versus tobramycin. 4. Number of exacerbations in the ensuing year and time to first pulmonary exacerbation following APE treatment. 5. Absolute change in Cystic Fibrosis Questionnaire-Revised (CFQ-R) respiratory domain score before and after APE treatment. 6. Number of episodes of neurotoxicity and ototoxicity in study arms, as noted on case-report forms. 7. Colistin peak, mid-point and trough during APE, for calculations of area under the curve (AUC).
PLANNED INTERIM ANALYSIS	When approximately 1/3 rd of patients have completed the study, an interim analysis for safety and outcome measures will be conducted. Serious adverse events will be monitored by the Medical Monitor on an ongoing basis throughout the study.

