5. CRITERIA FOR EVALUATION

5.1 Primary Endpoints

1. Absolute change in FEV₁ % predicted with standard colistin TID dosing versus PK-adjusted colistin BID dosing, with APE treatment.
2. Absolute change in FEV₁% predicted with standard tobramycin daily dosing versus PK-adjusted colistin BID dosing, with APE treatment.

3. Absolute change in FEV1% predicted with standard tobramycin daily dosing versus standard colistin TID dosing, with APE treatment.
4. Safety of standard colistin TID dosing versus PK-adjusted colistin BID dosing in APE treatment, based on assessments of clinical symptoms, AKI occurrences during treatment (based on KDIGO criteria), change in urine protein:creatinine ratios, and an FDA approved renal injury biomarker test, Nephrocheck®, which measures: TIMP2 and IGFBP-7 (Astute Medical).
5. Safety of standard tobramycin daily dosing versus PK-adjusted colistin BID dosing or standard colistin TID dosing in APE treatment, based on assessments described in #4.

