8.2 Blinding

Subjects and investigators will not be blinded to the use of tobramycin versus colistin. Measurement of tobramycin pharmacokinetics and adjustment of doses appropriately is standard clinical practice and cannot be modified for the study.

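### The synopsis and section 14 disagree on the number, trigger and purpose of the interim looks, and the protocol text gives no interim test level although one look is for early significance

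*Combined protocol and SAP*

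**What the plan says.** Three current statements describe the interim looks.

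- **Synopsis, Planned Interim Analysis.** When about one third of patients have completed the study, "an interim analysis for safety and outcome measures will be conducted".
- **Section 14, second paragraph.** "Efficacy will be evaluated in two planned interim analyses, each of which will occur after 1/3rd of the data is accrued". The sentence then offers an alternative trigger, that a third of subjects have finished dosing.
- **Section 14, third paragraph.** "When approximately 50% of patients have completed the study through Visit 4, an interim analysis for safety, futility, and early significance will be conducted".

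Section 14 opens with "A Data Safety and Monitoring Plan (DSMP) is in place for this study", but that plan is not among the documents.

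Sections 15.1 to 15.4 do not mention an interim analysis. Section 15.2 sets the default level: "Unless otherwise noted, 2-sided tests will be used with" alpha 0.05. The synopsis repeats it. Section 15.2 plans FEV1 as equivalence to within 5%. Section 15.3 compares adverse event rates by covariate-adjusted logistic regression.

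AKI is not only a monitoring variable. Section 5.1 includes "AKI occurrences during treatment (based on KDIGO criteria") in a primary safety endpoint, and section 15.4 rests the sample size of 30 per group on colistin's superiority for safety. On masking, section 8.2 says: "Subjects and investigators will not be blinded to the use of tobramycin versus colistin".

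**The concern.** Someone following the protocol cannot tell how many looks to run, when to run them, or what each may conclude. Section 14 conflicts with the synopsis and is unclear within itself. The word each does not separate the two efficacy looks in time, the word or gives them two triggers, and nothing says whether the 50% look is an additional one.

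The 50% look is the only one that names significance, and the protocol text attaches no test level, endpoint or futility rule to it. Because FEV1 is planned as an equivalence comparison, it is also unclear whether an early finding would mean equivalence or a difference. A safety look that formally compares the arms on AKI would be a look at a primary endpoint.

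The trial is single-centre and open as to tobramycin versus colistin. Unless the monitoring plan settles these points, which look counts could be decided after results are known. Testing at 0.05 at both an early look and the end can also raise the chance of a false claim.

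**Working it through.** **1. The passages side by side**

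| Place | Number | Trigger | Purpose |
|---|---|---|---|
| Synopsis | 1 | about 1/3 of patients completed (30 of 90) | safety and outcome measures |
| Section 14, 2nd paragraph | 2 | each after 1/3 of data, or 1/3 of participants dosed | efficacy |
| Section 14, 3rd paragraph | 1 | about 50% through Visit 4 (45 of 90) | safety, futility, early significance |
| Section 15 | none mentioned | none | none |

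This conflict does not depend on any error rate.

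**2. The plan's own figure.** The plan states no interim error rate, so there is none to reproduce. A single final test at |Z| > 1.96 returns the stated 0.05.

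**3. Difference test at 0.05 at the 50% look and at the end.** The two statistics have correlation √0.5 = 0.707. Overall error = 1 − P(|Z₁| ≤ 1.96 and |Z₂| ≤ 1.96) = 0.083. With the synopsis look at 1/3 in its place, the correlation is √(1/3) = 0.577 and the error is 0.088. FEV1 is not planned as a difference test, so these figures only give the scale.

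**4. FEV1 equivalence.** Inputs are a margin of 5 (taken as points of FEV1 % predicted), 15 per arm at the look, 30 per arm at the end, and a true difference at the margin. The documents give no SD of change, so the SD is assumed. Equivalence is declared if the t-based CI lies within ±5. The method is simulation with equal arms and no covariates. The documents do not say whether a 95% or a 90% CI is meant.

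| Assumed SD | 95% CI: final only → with 50% look | 90% CI: final only → with 50% look |
|---|---|---|
| 5 | 2.5% → 4.2% | 5.0% → about 8.0% |
| 7 | 2.5% → 3.2% | 5.0% → 7.4% |
| 9 | 1.5% → 1.6% | about 4.5% → 5.1% |
| 12 | about 0 throughout | 0.8% → 0.9% |

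**5. AKI.** Exact enumeration with equal risks of 12% to 19% (the retrospective rates in section 1.1), 0.05 at each look and no covariates:

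- Fisher's test: 1.3% to 2.1% at the end alone, 1.9% to 3.3% with a 50% look.
- Unadjusted Wald test: at most 4.6% with any set of looks examined.
- Pearson test, which the plan does not name: 4.9% to 5.5% at the end alone, 7.5% to 8.2% with a 50% look.

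The effect therefore depends on the test. The planned covariate-adjusted model was not simulated.

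A Fisher-only illustration for tobramycin against standard colistin shows how few events a look at 15 per arm would hold. Expected events are 15 × 0.19 + 15 × 0.12 = 2.85 + 1.80 = 4.65. A split of 4 v 0 gives p = 0.10 and 5 v 0 gives p = 0.042, so significance needs a difference of at least 5/15 = 33 points. At 19% v 12% the chance is 2.6%, and the observed difference then averages 37 points against an assumed 7. With an unadjusted Wald test the chance is 0.5%. The documents give no AKI rate for the PK-adjusted arm.

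**6. Limits that control the error for one look at 50% (O'Brien-Fleming).**

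- Two-sided 0.05: final Z = 1.977 and look Z = 1.977 × √2 = 2.80, so p = 0.048 and 0.005. The rounded pair gives 0.0499 overall. The matching CIs are 99.5% and 95.2%.
- One-sided 0.05, to match a 90% CI: Z = 2.373 and 1.678, so CIs of 98.2% and 90.7%, with 0.050 overall.
- False equivalence with these limits is about 2.5% (95% scale) and 5.0% (90% scale) at SD 5, and lower at larger SDs.

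**The case against.** The strongest reply has four parts.

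- **The missing rules may exist.** A monitoring plan is said to be in place and could hold boundaries. This stands, so the finding covers the protocol text only. That plan cannot, however, make the synopsis and section 14 agree.
- **The harm is conditional.** The rates apply only if an interim look may declare success at 0.05, which the documents do not say. With a 95% CI the equivalence error stays below 5%, and for AKI the Fisher and Wald rates do too. This also stands. The point is chiefly a conflict in the text, with a modest possible effect on error.
- **Interim review is legitimate.** Futility stopping does not inflate type I error, and limiting the looks to safety is a design preference. This stands, so the looks need not be removed.
- **The largest rates need an extra assumption.** A reader might infer looks at 1/3 and 2/3 (10.7%), or at 1/3, 1/2 and 2/3 (12.0%), each plus the final. No passage gives a look at 2/3. Those figures need each to mean successive thirds, and they are for a difference test that is not planned for FEV1.

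**Conclusion.** The concern holds as an inconsistency that should be fixed. Number, trigger and purpose differ between the synopsis and section 14, section 15 does not mention interim looks, and the look for early significance has no level, endpoint or futility rule in the protocol text.

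Its size, per contrast, if the 50% look and the final are both tested at 0.05, is 8.3% for a generic difference test. For FEV1 equivalence the error rises by about 1.7 points (95% CI) or 3 points (90% CI) at SD 5, and by well under 1 point at SD 9. The SDs, equal arms and absence of covariates are assumptions. The three pairwise contrasts raise a separate multiplicity question that is not counted here.

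A reader might conclude that the trial's error rate is 12%, that interim AKI testing must exceed 5%, or that no interim rules exist anywhere. The documents support none of these. The first rests on an assumed 2/3 look and an unplanned test. The second fails for Fisher and Wald tests and is untested for the planned model. The third cannot be known without the monitoring plan.

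**What to change.** State one interim schedule, with the same number, trigger, purpose and endpoints, in the synopsis and in sections 14 and 15. Then choose one of two routes.

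- **If a look may declare early significance:** give it a level that controls the overall error for each contrast. For a single look at 50%, O'Brien-Fleming limits are two-sided p < 0.005 at the look and p < 0.048 at the end. For FEV1 equivalence, first state the intended CI level. Then use 99.5% and 95.2% CIs if 95% is intended, or 98.2% and 90.7% if 90% is intended.
- **If no early claim is intended:** delete early significance and say that interim looks cannot declare success on FEV1 or AKI. The final 0.05 then stands.

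Futility review may stay on either route, with its rule stated or the monitoring plan cross-referenced. If that plan already holds rules, bring them into section 14.

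The cost is wording, plus one of the following:

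- **Look kept, limits matched to the intended CI:** at 30 per arm with no true difference, equivalence power falls from 55% to 54% (SD 7) and from 14% to 13% (SD 9) on the 95% scale. On the 90% scale it falls from 72% to 71% (SD 7) and from 37% to about 34-35% (SD 9). That is about 1 to 3 points at assumed SDs.
- **Early claim given up:** little is lost at SD 7 or more. At 15 per arm with no true difference, early equivalence has a 4.4% chance at SD 5 and about 0 at SD 7 with a 99.5% CI. With a 98.2% CI the chances are 22% and 0.5%.

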4. STUDY DESIGN

4.1 Study Overview

This is a prospective randomized single center interventional trial enrolling adult CF subjects who are diagnosed with acute pulmonary exacerbations (APE) by their treating

physician and who, according to their treating physician, will receive either tobramycin or colistin for the treatment of *Pseudomonas aeruginosa* or other appropriate gram-negative rods, such as *Achromobacter xylosoxidans*. The study is designed to evaluate a) whether pharmacokinetically adjusted colistin dosing, given on a twice daily schedule, provides a more favorable efficacy and safety profile versus standard colistin three times daily dosing, with no serum levels analyzed, b) whether pharmacokinetic-adjusted twice daily colistin dosing compares favorably to standard once daily tobramycin dosing, based on efficacy and safety, and c) how standard colistin dosing compares to standard once daily tobramycin dosing, based on efficacy and safety, during treatment of APE. The three treatment arms are as follows: 1) standard colistin TID dosing (based on product insert and evidence based recommendations for CF⁵), 2) pharmacokinetic-adjusted twice daily colistin dosing, or 3) standard tobramycin dosing once daily. The premise of the study is that newer, highly accurate analytical techniques, available through the University of Colorado School of Pharmacy have allowed pharmacokinetic (PK) and pharmacodynamic (PD) studies of colistin, in a cohort of adult CF subjects receiving the agent during APE. This has allowed us a new understanding of how the drug is metabolized in CF and how we can optimize its administration.

1. Adult patients will be enrolled at the time therapy is initiated for the treatment of a pulmonary exacerbation of CF.
2. Subjects will be block randomized based on gender, FEV₁%, and time of enrollment, into one of three treatment arms.
3. Patients receiving standard colistin dosing will be treated according to product insert and evidence based recommendations for CF². Patient demographics, medications, and results of standard laboratory tests will be recorded.

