6. SUBJECT SELECTION

6.1 Study population

Subjects with a diagnosis of CF who meet all the inclusion and none of the exclusion criteria will be eligible for participation in this study.

6.2 Inclusion criteria:

1. Male or female \geq 18 years of age at Visit 1.
2. Documentation of CF diagnosis as evidenced by one or more clinical features consistent with the CF phenotype and one or more of the following criteria:
 - Sweat chloride equal or greater than 60 mEq/L by quantitative pilocarpine iontophoresis test.
 - Two well-characterized mutations in the CFTR gene
 - Abnormal nasal potential difference (change in NPD in response to a low chloride solution and isoproterenol of less than -5 mV).
3. Documentation of the presence of an acute pulmonary exacerbation, based on CF Foundation guidelines, as diagnosed by a faculty member of the Denver Adult CF Program.
4. Respiratory culture(s) demonstrating evidence of *Pseudomonas aeruginosa* or *Achromobacter species* airway infection.
5. Subject is able to produce sputum, undergo phlebotomy, and provide written consent.
6. The subject's treating physician has determined that they should receive either tobramycin or colistin intravenously as one of the designated agents for their APE

treatment. Subjects who are able to receive either tobramycin or colistin as part of their antibiotic regimen will be randomized into one of three arms. If a treating physician deems that a subject cannot receive tobramycin due to vestibular toxicity, ototoxicity or bacterial resistance, the subject will be randomized to either standard or PK-adjusted colistin.

6.3 Exclusion criteria:

1. Presence of chronic renal insufficiency, with abnormal baseline creatinine >1.2mg/dL.
2. Presence of a condition or abnormality that in the opinion of the investigator would compromise the safety of the patient or the quality of the data.
3. Inability to perform reproducible spirometry.
4. Inability to expectorate sputum.

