8. STUDY TREATMENTS

8.1 Method of assigning subjects to treatment groups

All subjects will enter the study at the time they are diagnosed with an APE and designated for hospital admission to treat with a drug regimen which includes either intravenous tobramycin or colistin. Block randomization will be utilized based on gender, FEV₁% predicted, and time of enrollment to ensure relatively equal treatment allocation based on these variables.

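### The FEV1 covariates drop out of the pre-to-post contrast, the AKI model puts at least nine coefficients on about 13 events with its unit unstated, and neither model has a term for eligibility route

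*Combined protocol and SAP*

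**What the plan says.** **FEV1.** Section 15.2 targets the between-arm difference in pre-to-post change, tested for equivalence within 5%. The mixed model has a subject random intercept and "the following covariates: age, other medication, admits in the previous year, and diabetes". It goes on: "Nested random terms will be included in the model to account for repeated measures", at subject level and at visit level inside subject. Table 3 in section 9 schedules spirometry at Visits 1 and 4 only.

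**Allocation.** Section 4.1 states: "Subjects will be block randomized based on gender, FEV₁%, and time of enrollment, into one of three treatment arms". Section 8.1 repeats the factors: "Block randomization will be utilized based on gender, FEV₁% predicted, and time of enrollment".

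**AKI.** Section 15.3 speaks of incidence and compares event rates by logistic regression. The covariates are age, medications, baseline FEV1, prior-year admissions, "exposure to nephrotoxic antibiotics in the previous 5 years, and diagnosis of CF related diabetes (CFRD) as covariates". It adds: "Repeated measures within subjects will be accounted for by including a random intercept for subjects". Section 15.1 says "Subjects will be enrolled once".

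**Entry.** Under section 6.2, for a subject who "cannot receive tobramycin due to vestibular toxicity, ototoxicity or bacterial resistance, the subject will be randomized to either standard or PK-adjusted colistin". Section 2.1 also lets a subject for whom colistin is ruled out enter the tobramycin arm only. Section 6.2 does not list that route.

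**The concern.** The FEV1 model looks adjusted, but its covariates are characteristics of the subject, and the quantity of interest is a within-subject change compared between arms. Two of the three blocking factors, gender and enrolment time, are separately left out of section 15.2. Visit 1 FEV1 appears there only as half of the response, not as an adjustment covariate.

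AKI matters more, because section 15.4 says that safety is the more appropriate basis for sizing. The model there is large for the events expected. Its random intercept has a meaning only if each subject contributes several records, and section 15.3 does not say so. It names no test or interval method for the arm comparison either, so these choices could be made after the data are seen.

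Finally, subjects entering by a restricted route make the tobramycin-versus-colistin contrasts partly non-randomised, and neither model accounts for that. Section 1.1 shows that patients given the two drugs differed in the retrospective cohort: CFRD in 38% on tobramycin and 66% on colistin, and mean FEV1 of 50% and 40% predicted.

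**Working it through.** **1. Inputs.** 30 per arm (15.4). AKI 19% on tobramycin and 12% on colistin (1.1). Pilot FEV1 SD of 15 (1.1, Table 1). Assumed, because the documents give no value: the PK-arm AKI rate (12%, range 0 to 19%), the pre-post correlation r, covariate distributions, route shares and route effects. The plan's statement that AKI was 60% higher on tobramycin reproduces: 0.19/0.12 = 1.58. The plan gives no expected event count.

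**2. FEV1 cancellation.** Let Y = arm + visit + arm×visit + βx + u + e, with x and the subject effect u fixed within subject. Subtracting Visit 1 from Visit 4 leaves visit + arm×visit + (e4 − e1); βx and u are gone. With one value per visit, a visit-within-subject effect has the same subscript as e and cannot be separated from it. In a simulated trial of 90 subjects:

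| Model | Arm-by-visit estimate (SE) |
|---|---|
| No covariates | 3.109 (1.845) |
| Four listed covariates, all time-fixed | 3.109 (1.845) |
| Gender added as well | 3.109 (1.845) |
| 15% of post values missing, without covariates | 2.896 (1.947) |
| 15% of post values missing, with covariates | 2.941 (1.947) |

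The cancellation fails if Visit 1 means are constrained equal (2.557 without covariates, 2.787 with) or if covariate-by-visit terms are added (2.445). Section 15.2 specifies neither.

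**3. Precision forgone.** SE(change) = SD√(2(1−r))·√(2/30). SE(ANCOVA) = SD√(1−r²)·√(2/30). Their ratio is √((1+r)/2).
- r = 0.84: 2.19 to 2.10, a reduction of 4.1%.
- r = 0.7: 3.00 to 2.77, a reduction of 7.8%.

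The gain comes from Visit 1 FEV1. In the simulated trial above, that covariate alone cut the SE from 1.845 to 1.738; with gender and the four listed covariates added it was 1.852.

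**4. AKI events per coefficient.** Expected events are 30 × (0.19 + 0.12 + 0.12) = 12.9. With the PK arm at 0% this is 30 × 0.31 = 9.3, and at 19% it is 30 × 0.50 = 15.0. Coefficients are 1 intercept + 2 arm terms + 6 covariates = 9 at least. So 12.9/9 = 1.4 per coefficient (1.0 to 1.7).

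**5. Random intercept with one outcome per subject.** Take 4, 4 and 6 events in 30 and arm terms only. The maximised log-likelihood is −38.5725 at random-intercept SDs of 0, 1, 2 and 3, while the tobramycin coefficient drifts from 0.49 to 0.94. With six covariates the log-likelihood changes by 0.04 and the coefficient doubles, from 0.81 to 1.63.

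**6. Test behaviour.** Null simulation with 14.33% AKI in every arm, six null covariates and no random intercept, repeated at 4,000 to 6,000 trials per run:

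| Three-arm test, nominal 5% | Rejection |
|---|---|
| Likelihood ratio, all fits | 7.6% to 8.0% |
| Likelihood ratio, converged fits only | 5.7% to 5.8% |
| Wald | 2.2% to 2.5% |
| Firth, penalised likelihood ratio | 3.6% |

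About 4% to 5% of maximum-likelihood fits separate. At 19/12/12% the true log OR is ln[(0.19/0.81)/(0.12/0.88)] = 0.54. Maximum likelihood averages 0.62 (SD 0.90) and Firth 0.55 (SD 0.80).

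**7. Route and FEV1.** Assume 20% or 40% colistin-only entrants, starting 10 points lower, with no drug effect and no route effect on change. At 20%, 18 of 90 are colistin-only and each colistin arm has 24 + 9 = 33, so 9/33 = 27% are colistin-only and the Visit 1 gap between arms is 2.7. At 40% the share is 18/36 = 50% and the gap is 5. A baseline ANCOVA without route turns this into roughly (1−r) × gap: 0.16 × 2.7 = 0.4 up to 0.3 × 5 = 1.5. Simulation gives 0.4 to 1.4. The plan's change score stays within 0.04 of zero, and so does ANCOVA with route.

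**8. Route and AKI.** Assume the same shares, a route odds ratio of 2 and no drug effect. The mean tobramycin-versus-standard-colistin log OR is −0.24 (20%) and −0.39 (40%) without route, and −0.02 and 0.03 with it.

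**The case against.** Much can be said for the plan. Several stronger readings are tempting, and the documents do not support them.

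- A reader might infer that the FEV1 interval is invalid or carries a route bias. It is valid. Under the scenario examined, the false tobramycin difference of 0.4 to 1.4 points arises only in a baseline ANCOVA that omits route, which the plan does not propose.
- A reader might infer that gender and enrolment time go unused because of the cancellation. They are unused because section 15.2 omits them; as main effects in that model they would cancel too. Baseline FEV1 is not ignored either: it is in the FEV1 response and is a covariate for AKI.
- A reader might conclude that the random intercept is plainly wrong. Section 15.3 refers to repeated measures, section 10 records creatinine daily, and section 5.1 counts AKI occurrences. A record-level model could support the term. Incidence and single enrolment point the other way. The firm defect is that the unit is not stated.
- The likelihood-ratio excess comes mostly from separated fits, and the simulations omit the planned random intercept. The maximum-likelihood bias is small: (0.62 − 0.54)/0.90, about a tenth of an SD.
- The AKI route bias rests on shares and an odds ratio found nowhere in the documents. When route risk is assumed to act entirely through five-year nephrotoxic exposure, already a covariate, the bias is about zero.
- Restricting tobramycin contrasts to three-way subjects costs precision and leaves fewer AKI events.

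All of this stands, and it limits the size of the point. It does not restore the FEV1 adjustment, supply the missing unit and test, or make the tobramycin contrasts fully randomised.

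**Conclusion.** The point holds in three limited parts and should be settled before data are seen.

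1. **FEV1.** In the usual unconstrained arm-by-visit model, the time-fixed covariates adjust almost nothing. This assumes that 'other medication' is one value per subject, which section 15.2 leaves open. The loss is precision only: about 4% to 8% of the SE at r of 0.84 to 0.7.
2. **AKI.** About 13 events (9 to 15) carry at least nine coefficients. If AKI is one outcome per subject, the random intercept is not identifiable. With no test named, the null rejection rate runs from about 2.5% to 8% depending on the test and on how separated fits are scored.
3. **Route.** Tobramycin contrasts are partly non-randomised by design. The size and even the presence of a resulting bias depend on unknown shares and effects.

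**What to change.** - **FEV1:** replace the mixed model with ANCOVA of change (end of treatment minus Visit 1) on arm, Visit 1 FEV1, gender, enrolment block, the plan's baseline covariates and eligibility route, without random terms. Route is essential once Visit 1 FEV1 is a covariate (working, step 7). The plan gives no block size, so fix the coding of enrolment time in advance and keep it coarse. State how a missing Visit 4 is handled, so that the intent-to-treat set is kept: for example, early-termination spirometry (section 10.5), then multiple imputation from the same covariates.
- **AKI:** one outcome per subject, no random intercept, and Firth logistic regression with penalised-likelihood tests and profile intervals named in the SAP. If records by visit or day are intended, say so and state that the odds ratio is then per record.
- **Medication covariates:** in both models, only drugs in place before the first study-drug dose.
- **Route:** record it at allocation and reconcile sections 2.1 and 6.2 on tobramycin-only entry. Estimate colistin versus colistin from all subjects in those arms with a route term. For tobramycin contrasts, use subjects randomised among all three arms, or all randomised subjects with a route term. Describe tobramycin-only entrants separately, and report AKI counts by arm and route.

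**Cost:** SAP wording, a few lines of SAS and one recorded variable. Firth is slightly conservative (about 4% at nominal 5%). With 20% to 40% colistin-only entrants, three-way-only tobramycin contrasts have an FEV1 SE 0 to 12% larger (for example 2.44 to 2.73 at 40%, r = 0.84). They rest on about 10 or 8 AKI events, close to one per coefficient, so the covariate list may need cutting there. The colistin-versus-colistin FEV1 SE falls by about 3% to 7%.
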